**1. Active surveillance of maternal side effects and medical complications associated with aspirin:**

Maternal surveillance will be composed of active assessment of unintended medical visits. Likewise, where obtained for clinical care, hemoglobin will be recorded as well as administration of both oral and intravenous iron. Likewise the incidence of postpartum hemorrhage, antepartum hemorrhage, cesarean delivery and maternal death due to postpartum hemorrhage will likewise be monitored on an ongoing basis.

**2. Evaluation of fetal side effects:** If occurrences of major fetal abnormalities or fetal loss are discovered during ultrasound procedures or follow-up visits, they will be noted and the woman will be referred according to local standard of care. Likewise, stillbirth and late abortion (delivery between 16 and 20 weeks) will be monitored via established maternal and newborn health

registry that is conducted within the Global Network infrastructure at each site. Fetal anomalies and loss will also be reviewed at least twice a year by the Data Monitoring Committee (DMC)

3. **Evaluation of changes in maternal hemoglobin:** Anemia will be monitored in all women, with sequential hemoglobin measurements at randomization and again between 26-30 weeks GA. Women with hemoglobin < 7.0 g/dl at randomization will be excluded from the study. Hemoglobin will also be measured at 4 weeks post-randomization in the first 500 available women who agree to participate, with changes in hemoglobin assessed by treatment group. Recognizing that site-specific characteristics may affect maternal hemoglobin, the 500 woman sample will include at least 50 women from each site. Women with hemoglobin levels of < 7.0 g/dL or with a change of more than 3.5 g/dl when measured post-randomization will be referred to a health provider to receive the local standard of care.

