Late Abortion	Binary	
The unit of analysis will be individual woman. Per the protocol, late abortion is defined as: "Spontaneous fetal loss <math>\geq</math> 16 weeks." This outcome will be defined based on a response of 4 for Question A7 from Form MN02 from the MNH registry and will be classified as "Yes" if that response is listed as the Mode of Delivery and the pregnancy has a GA of 16 weeks or greater and "No" otherwise. Per the MNH Registry Manual of Operations, that mode of delivery should be used if "A delivery prior to 20 weeks gestation (or <500 g). Miscarriage is also known as spontaneous abortion." If the delivery is after 20 weeks and is classified as a miscarriage on the form, the outcome will be reclassified as a stillbirth. Individuals with loss prior to 16 weeks will be excluded from the analyses.
 
Analysis population: ITT

Variable	Type	Definition
Other Outcomes of Interest—Fetal Outcomes		
Preterm birth <34 0/7 weeks of pregnancy	Binary	
The unit of analysis will be the individual delivered fetus or infant (either live birth or stillbirth); note that per the protocol, the event is defined as: “live birth before 34 0/7 weeks of pregnancy are completed,” so this definition represents a departure from the protocol. This will be defined as a secondary variable in the analysis data set based on gestational age as determined from ASP forms and neonatal outcome as determined from Form MN02 from the MNH Registry.
 
Analysis population: mITT

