Fetal Loss	Binary	
The unit of analysis will be the individual delivered fetus or infant and per the protocol, the event of fetal loss is defined as: "Spontaneous loss <math>\geq</math> 16 weeks GA plus perinatal mortality." This binary outcome measure will be defined in the analysis data set based on gestational age as measured via the ASP forms and mortality outcomes as determined from Forms MN02 and MN03 from the MNH Registry. Any death of an infant greater than 16 weeks GA and prior to 7 days post-delivery will be classified as "Yes" and live births classified as alive at 7 days will be classified as "No." Any fetal loss (including MTP or miscarriage) that occurs prior to 16 weeks will be treated as a missing value.
 
Analysis population: ITT

Variable	Type	Definition
Spontaneous abortion	Binary	
The unit of analysis is the individual pregnancy. Per the protocol, the binary outcome of spontaneous abortion is defined as: "Premature expulsion of a non-viable fetus from the uterus at < 20 weeks gestation." This outcome will be defined based on Questions A7-4 or C1 from Form MN02 from the MNH registry and will be classified as "Yes" if the response to A7-4 is listed as the Mode of Delivery or the response to C1. Fetal/Neonatal outcome is answered 1. Miscarriage and "No" otherwise. Per the MNH Registry Manual of Operations, that mode of delivery should be used if "A delivery prior to 20 weeks gestation (or <500 g). Miscarriage is also known as spontaneous abortion."
 
Analysis population: ITT

Stillbirth	Binary	
The unit of analysis will be the individual infant that delivers at 20 weeks gestational age or greater during the specified analysis period. The event will be classified as "Yes" if the infant is classified as a non-macerated still birth or with maceration status unknown via Forms MN02 and MN05 in the MNH Registry and "No" if the baby is born alive as specified via Form MN02 in the MNH Registry. Note that infants classified as Macerated still births are not included in this population. Also note that deliveries classified as miscarriages but that have GA of 20 weeks or greater will be reclassified as stillbirths.
 
Analysis population: mITT

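### SAP 9.2 scores Late Abortion from the mode-of-delivery item alone, so a 16–19 week loss coded as miscarriage only on the fetal-outcome item would count as a non-event

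*Combined protocol and SAP*

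**What the plan says.** Protocol Appendix 3 defines late abortion as a spontaneous fetal loss at 16 weeks or later. Protocol 2.8 gives the window and the purpose, under evaluation of fetal side effects: "stillbirth and late abortion (delivery between 16 and 20 weeks) will be monitored" through the registry.

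The SAP 9.2 row for Late Abortion repeats the Appendix 3 definition and then turns it into a coding rule: "This outcome will be defined based on a response of 4 for Question A7 from Form MN02 from the MNH registry". The outcome is Yes "if that response is listed as the Mode of Delivery and the pregnancy has a GA of 16 weeks or greater", and No in all other cases. Item C1 is not mentioned. The row also quotes the registry manual, which assigns mode 4 to deliveries before 20 weeks or under 500 g. Two further rules set the limits. At the upper end, "If the delivery is after 20 weeks and is classified as a miscarriage on the form, the outcome will be reclassified as a stillbirth". At the lower end, losses before 16 weeks are left out of the analysis. The population is ITT.

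The SAP 9.2 row for Spontaneous abortion uses two items: "This outcome will be defined based on Questions A7-4 or C1 from Form MN02 from the MNH registry". Either the miscarriage response on A7 or response 1 (Miscarriage) on C1 is enough for a Yes. The MTP row has the same structure: response 5 on A7 or response 2 on C1.

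**The concern.** Late Abortion is, in substance, the part of Spontaneous abortion that falls at 16–19 weeks. A subset should not have a narrower case definition than the set it belongs to, apart from the gestational age limits. By accepting either item for Spontaneous abortion and for MTP, the SAP provides for one item recording a loss that the other does not. For Late Abortion that provision is missing, and the catch-all No turns such a record into a non-event instead of a missing value or a query.

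What is at stake is how completely one exploratory outcome is counted. The protocol names that outcome among the fetal events it will monitor. The primary analysis and the sample size do not use it.

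**Working it through.** **1. Rules side by side.** Take a loss at 16–19 weeks by study dating, with no MTP code on either item, and apply the rules as written:

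| A7 | C1 | Spontaneous abortion | Late Abortion |
|---|---|---|---|
| 4 | 1 | Yes | Yes |
| 4 | not 1 | Yes | Yes |
| not 4 | 1 | Yes | **No** |

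Only the third row is discordant. Fetal Loss is also Yes for that record, because its rule covers any death beyond 16 weeks whatever the A7 code. The woman remains in the Late Abortion denominator, since only losses before 16 weeks are removed.

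**2. Is it repaired elsewhere?** SAP 12 (changes from the protocol) neither lists nor explains the omission of C1. The masked review in SAP 7.6 covers the per-protocol population, the primary outcome and selected secondary outcomes. Late Abortion is classed as an other outcome of interest in SAP 3.3. Protocol 3.6 and SAP 4.4 provide for data editing and query resolution, but neither names a check of A7 against C1.

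**3. How many records?** The plan gives no rate for Late Abortion and no A7/C1 disagreement rate, so there is no planned figure to reproduce. An illustration:

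missed events = N × L × s × d

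- N = 11,920 women (SAP 4.3).
- L = 2% to 8% pregnancy loss before 20 weeks (SAP 7.3).
- s = share of those losses at 16–19 weeks, **assumed** 10% to 30%.
- d = share of those coded as miscarriage on C1 but not on A7, **assumed** 0% to 20%.

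| L | s | Losses at 16–19 weeks | d = 0% | d = 5% | d = 10% | d = 20% |
|---|---|---|---|---|---|---|
| 2% | 10% | 23.8 | 0 | 1.2 | 2.4 | 4.8 |
| 5% | 20% | 119.2 | 0 | 6.0 | 11.9 | 23.8 |
| 8% | 30% | 286.1 | 0 | 14.3 | 28.6 | 57.2 |

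In the middle row, for example, 11,920 × 0.05 × 0.20 = 119.2, and 119.2 × 0.10 = 11.9. The range is 0 to about 57 for the whole trial.

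**4. Effect on the reported rate (middle row).** Losses before 16 weeks number 11,920 × 0.05 × 0.80 = 476.8. Ignoring loss to follow-up, the denominator is 11,920 − 476.8 = 11,443.2. The true rate is 119.2 / 11,443.2 = 1.04%. With d = 10% it is reported as (119.2 − 11.9) / 11,443.2 = 0.94%.

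**5. Effect on the comparison.** Suppose a fraction 1 − d of true events is captured in each arm, with no false positives. The missed women stay in the denominator, so the expected relative risk is [(1 − d)p₁] / [(1 − d)p₀] = p₁/p₀, which is unchanged. The risk difference shrinks by the factor 1 − d. For a rare event, the standard error of the log relative risk grows by about 1/√(1 − d), which is 1.05 at d = 10% and 1.12 at d = 20%.

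**The case against.** The strongest reply is the manual text that the SAP itself quotes in the Late Abortion row. If registry staff follow it, every spontaneous loss at 16–19 weeks carries A7=4, including one expelled vaginally, and the third row of the rule table is empty. A discordant record then needs a coding error, and routine data checks may catch it. This stands. It is why the number may be zero, and why the point concerns what the rule would do and not what it has done.

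Two further replies also stand. The losses do not vanish from reporting, because the same record is Yes for Spontaneous abortion and for Fetal Loss. SAP 9.6 treats these outcomes as exploratory.

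What survives is that the SAP accepts C1 for the two neighbouring outcomes taken from the same form and gives no reason for leaving it out here.

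A reader might infer more, in three ways that the documents do not support:

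- **That losses at this stage are especially likely to carry an ordinary delivery mode, so the error concentrates on this outcome.** No document says so, and the manual instruction points the other way.
- **That registry stillbirths dated below 20 weeks by the study forms belong to the same fault.** They are a different matter, namely registry outcome against study dating. Adding C1=1 would not move them. Adding a stillbirth route to Late Abortion alone would create a new mismatch, because Spontaneous abortion has no such route.
- **That Table 5a must contradict itself.** Its rows use different units and gestational windows, so their totals need not agree.

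**Conclusion.** The inconsistency is real and can be read directly from SAP 9.2. A 16–19 week spontaneous loss with C1=1 and A7 other than 4 would be scored as a non-event for Late Abortion while counting as a Spontaneous abortion. Nothing elsewhere in the plan is stated to correct it.

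Its size cannot be determined from the documents. The range of 0 to about 57 events rests on an assumed timing of losses and an assumed disagreement between items, and zero is a legitimate value. It would therefore be wrong to conclude that the Late Abortion rate is understated; it would be understated only if such records exist.

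A reader might also infer a biased treatment comparison. SAP 4.4 keeps research staff and local providers masked. If registry coding was masked in the same way, under-capture should be similar in the two arms and the expected relative risk is preserved. The cost would be a lower reported rate, a smaller absolute difference and some loss of precision. The primary test and the sample size are untouched. Severity is minor.

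**What to change.** Reword the Late Abortion row in SAP 9.2 as follows: Yes if A7=4 or C1=1, with no MTP code on either item (A7 not 5 and C1 not 2), and study gestational age from 16 0/7 to 19 6/7 weeks. The A7-or-C1 part is then the same as for Spontaneous abortion. The MTP condition keeps the outcome to spontaneous losses; stating it in the Spontaneous abortion row too would keep one outcome nested in the other. If C1 was left out on purpose, give the reason and say how discordant records are resolved.

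Do not add registry stillbirths to this definition alone. If registry stillbirths with study gestational age below 20 weeks are to be reclassified, write one rule and apply it to Spontaneous abortion and Late Abortion together.

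The cost is a sentence or two of SAP text and a small change to the derivation code. Both items are already on Form MN02, so no new data are needed. A cross-tabulation of A7 against C1 for losses at 16–19 weeks, pooled over arms and run before unmasking, would show whether the change moves any record.

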### **FETAL OUTCOMES OF INTEREST**

- ***Preterm birth <34 0/7 weeks of pregnancy:*** live birth before 34 0/7 weeks of pregnancy are completed.

- **Birth weight <2500g and Birth weight <1500g:** Birth weight is defined as the first weight of the fetus or newborn obtained after birth. For live births, birth weight should preferably be measured within the first hour of life before significant postnatal weight loss has occurred, recorded to the degree of accuracy to which it is measured (WHO). Birth weight <2500 g is defined as low birth weight, whereas birth weight <1500 g is defined as very low birth weight.
- **Fetal Loss:** Spontaneous loss  $\geq$  16 weeks GA plus perinatal mortality.
- **Late abortion:** Spontaneous fetal loss  $\geq$  16 weeks.
- **Spontaneous abortion:** Premature expulsion of a non-viable fetus from the uterus at  $<$  20 weeks gestation.
- **Stillbirth:** Birth of a baby that shows no signs of life at birth (no gasping, breathing, heart beat or movement). (WHO). It may be a macerated or fresh stillbirth. The signs of maceration are discoloration and peeling of the skin leaving areas of raw tissue. The skull is usually soft, as the brain has become soft. The umbilical cord is usually stained a dark red or black. The amniotic fluid is usually darkly stained. Maceration is the result of the infant being dead for at least 12 hours. Macerated stillborn infants are assumed to have died before the onset of labor. Fresh stillbirths show no sign of maceration and have usually died during labor or shortly before the onset of labor.
- **Medical termination of pregnancy:** an operation or other procedure to terminate pregnancy before the fetus is viable.

**NOTE:** (WHO) at the end of the definition means the definition is from the 2006 WHO guide titled: *Integrated Management of Pregnancy and Childbirth Pregnancy, Childbirth, Postpartum and Newborn Care: A guide for essential practice.*

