Antepartum Hemorrhage	Binary	
The unit of analysis will be individual woman with a delivery after 22 weeks. Per the protocol, antepartum hemorrhage is defined as: “Bleeding from the genital tract at any time after the 22nd week of pregnancy and before the birth of the baby. There are two main causes of antepartum hemorrhage, placenta previa and abruptio placentae.” This outcome will be defined based on Question A8b from Form MN02 from the MNH Registry. The event is defined as follows in the MNH Registry Manual of Operations: “Defined as blood loss of > 1000 cc of blood prior to delivery.”
 
Analysis population: mITT

Variable	Type	Definition
Postpartum Hemorrhage	Binary	
The unit of analysis will be individual woman. Per the protocol, postpartum hemorrhage is defined as: "Blood loss of 1000 ml or more from the genital tract after delivery and up to six weeks post-delivery. Common causes include atony (poor muscle tone) of the uterus or trauma to the genital tract, e.g. tears of the vagina, cervix, or lower segment of the uterus." This outcome will be defined based on Question A8c from Form MN02 or Question B7 from Form MN03 from the MNH Registry. The event is defined as follows in the MNH Registry Manual of Operations: Defined as blood loss of > 1000 cc of blood after delivery prior to six-week visit.
 
Analysis population: Safety

Maternal mortality through 42 days	Binary	
The unit of analysis will be women randomized. Per the protocol, maternal mortality is defined as: "the death of a woman during pregnancy (i.e. conception to delivery) and the puerperium (i.e. up to 42 days after delivery)." The event will be defined as "Yes" if the woman dies prior to 42 days after delivery and "No" otherwise. This outcome measure will be obtained from forms MN02 and MN03 in the MNH Registry. If the 42-day outcome is missing and the woman was alive at the last known follow-up, this outcome will be treated as missing.
 
Analysis population: ITT

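### Some SAP 9.2 coding rules for exploratory pregnancy-loss outcomes do not match the definitions they quote and can misclassify women

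*Combined protocol and SAP*

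**What the plan says.** Four rows of the SAP 9.2 variable table are at issue: spontaneous abortion, late abortion, fetal loss and MTP. SAP 3.3 lists all four as other outcomes of interest, and each is assigned to the ITT population.

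*Spontaneous abortion.* The row repeats the definition in protocol Appendix 3, which begins "Premature expulsion of a non-viable fetus from the uterus at" and limits the event to under 20 weeks. The operative rule is Yes "if the response to A7-4 is listed as the Mode of Delivery or the response to C1" is miscarriage, and No for everything else. The row also cites the registry manual, which gives the miscarriage code to a delivery before 20 weeks or under 500 g.

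*Stillbirth and late abortion.* The stillbirth row says that "deliveries classified as miscarriages but that have GA of 20 weeks or greater will be reclassified as stillbirths". The late-abortion row says: "If the delivery is after 20 weeks and is classified as a miscarriage on the form, the outcome will be reclassified as a stillbirth". The spontaneous-abortion row has no such sentence.

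*Fetal loss.* The quoted definition is spontaneous loss at 16 weeks or later plus perinatal mortality. The rule is: "Any death of an infant greater than 16 weeks GA and prior to 7 days post-delivery will be classified as" Yes. A No requires a live birth known to be alive at 7 days. Losses before 16 weeks, with MTP named among them, are set to missing.

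*Default values.* Spontaneous abortion, late abortion and MTP are No unless the Yes condition is met, and none has a missing category (late abortion excludes losses before 16 weeks). Other rows do have one. Vaginal bleeding is missing when there is no biweekly form, and for maternal mortality: "If the 42-day outcome is missing and the woman was alive at the last known follow-up, this outcome will be treated as missing".

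**The concern.** In each row the rule that a programmer would code is wider or looser than the definition beside it. The same woman can appear under two outcomes that are meant to be exclusive, an induced event can enter a composite defined by spontaneous loss, and an unknown outcome can be recorded as a non-event.

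These rows matter because the primary analysis conditions on reaching 20 weeks. SAP 9.4 treats earlier losses as missing completely at random, while SAP 7.3 accepts that women with early losses may differ in risk. The spontaneous-abortion and MTP lines of Table 5a compare those losses by arm, with a relative risk and a p-value. If the spontaneous-abortion count includes deliveries at 20 weeks or later, it need not match the losses removed from the mITT population, which SAP 5 defines by gestational age at delivery.

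**Working it through.** **Test cases under the literal rules of SAP 9.2**

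| Case | Spontaneous abortion | Late abortion | MTP | Fetal loss | Stillbirth |
|---|---|---|---|---|---|
| Miscarriage code, 14 weeks | Yes | Excluded | No | Missing | Not in population |
| Miscarriage code, 16 0/7 weeks | Yes | Yes | No | Unassigned | Not in population |
| Miscarriage code, 18 weeks | Yes | Yes | No | Yes | Not in population |
| Miscarriage code, 21 weeks, under 500 g | **Yes** | Moved to stillbirth | No | Yes | **Yes** |
| MTP, 14 weeks | No | Excluded | Yes | Missing | Not in population |
| MTP, 18 weeks | No | No | Yes | **Yes, by implication** | Not in population |
| Lost at 15 weeks, no outcome form | **No** | **No** | **No** | Unassigned | Not in population |
| Live birth, 39 weeks | No | No | No | No | No |

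- *21-week case.* The code alone triggers spontaneous abortion, and the stillbirth row then reclassifies the delivery. Its Yes for fetal loss is intended, because fetal loss is a composite that includes perinatal death.
- *18-week MTP.* The Yes rule omits the word spontaneous. The next sentence treats MTP as a kind of fetal loss and removes it only before 16 weeks.
- *16 0/7 weeks.* The rule covers deaths above 16 weeks and sets losses before 16 weeks to missing, so neither part reaches this case. The definition does include it.
- *Lost at 15 weeks.* Three rows give No. Fetal loss does not, because its No needs a live birth known alive at 7 days.

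**Scale of the default No**

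Inputs from SAP 6.1: 5,483 evaluable women per arm, an 8% allowance, and loss to follow-up of 1-2%. From SAP 7.3: loss before 20 weeks in 2-8% of women. SAP 6.1 plans on about 5%.

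Plan's denominator: 5,483 / (1 - 0.08) = 5,960 per arm, and 2 x 5,960 = 11,920, as stated.

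Women without an outcome, if every woman lost has no outcome form:
- 1%: 0.01 x 5,960 = 60 per arm; 0.01 x 11,920 = 119 in all
- 2%: 0.02 x 5,960 = 119 per arm; 0.02 x 11,920 = 238 in all

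Scored risk = true risk x (1 - loss to follow-up), assuming that women lost have the same risk as the others:

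| True risk | Scored at 1% loss | Scored at 2% loss |
|---|---|---|
| 2% | 1.98% | 1.96% |
| 5% | 4.95% | 4.90% |
| 8% | 7.92% | 7.84% |

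Factor applied to the relative risk = (1 - loss, aspirin) / (1 - loss, placebo):
- equal loss: 1
- 2% aspirin, 1% placebo: 0.98 / 0.99 = 0.990
- 1% aspirin, 2% placebo: 0.99 / 0.98 = 1.010

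The documents give no rate of miscarriage codes at 20 weeks or later, and none of MTP at 16 weeks or later. The size of the double count and of the MTP misclassification therefore cannot be computed.

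**The case against.** **Double counting.** A reader might infer that the SAP does count losses at 20 weeks or later twice. It does not say so. Two rows state the reclassification, and the late-abortion wording can be read as a recode of the record before any outcome is derived. The spontaneous-abortion row also quotes the limit of under 20 weeks. A double count arises only if the recode is not applied upstream. That stands as a reason to say *can*. It does not remove the gap, because the SAP never says that the recode comes first, and the rule omits the limit.

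**Terminations.** No sentence scores MTP at 16 weeks or later as Yes, and the row opens with spontaneous loss. The reading is an implication. It is a strong one, because the missing-value rule treats MTP as fetal loss, and the hypertensive-disorders row excludes MTP in words where that is meant.

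**Default No.** The No could mean any other answer on a completed form. SAP 5 provides for imputation in the ITT set, and SAP 7.3 for multiple imputation when more than 2% is missing. Neither is said to override the row, and a value already scored No leaves nothing to impute. A reader might also take 119-238 as the number wrongly scored. It is an upper bound: a woman seen still pregnant past 20 weeks and then lost is correctly No for spontaneous abortion, and the biweekly and blood-pressure visits can show this.

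**Importance.** These outcomes are exploratory (SAP 9.6). Table 2 also shows miscarriage and MTP by arm, and SAP 7.3 plans two sensitivity analyses for early loss. This stands and limits the weight of the point.

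**Conclusion.** The point holds as a mismatch between coding rules and quoted definitions in a few exploratory outcomes. Followed literally, the rules can count a miscarriage-coded delivery at 20 weeks or later under two headings, count later MTP as fetal loss by implication, leave a loss at 16 0/7 weeks without a value, and score unknown status as No for spontaneous abortion, late abortion and MTP. The last does not apply to fetal loss.

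Only the default No can be sized: at most 119-238 women, an understatement of risk by at most 1-2% in relative terms, and a change in the relative risk of none to about 1%. This rests on the planned 1-2% loss to follow-up, on all such women lacking an outcome form, and on their having the same risk as the rest.

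A reader might infer that the primary result is at risk. The documents do not support that: mITT membership and preterm birth depend on gestational age at delivery, not on the miscarriage code. The point is minor and worth correcting because it is cheap.

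**What to change.** In SAP 9.2, or in the addendum that SAP 7.6 provides for before data lock:

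1. Spontaneous abortion: add *and GA below 20 0/7 weeks* to the Yes rule. State that reclassification of miscarriage codes to stillbirth is applied before any outcome is derived.
2. Fetal loss: use *16 0/7 weeks or later* in the Yes rule, and state that MTP at or after 16 weeks is not counted as spontaneous loss. Say whether those pregnancies are then No or missing. The row already sets earlier MTP to missing, but doing the same later removes women on a post-randomisation event, so the choice should be written down.
3. Spontaneous abortion, late abortion and MTP: set to missing only when there is no outcome record *and* study visits do not show the pregnancy continuing past the relevant gestational-age limit (20 weeks for the first two). The MTP definition refers to viability and gives no week, so name the limit used. Setting every woman without a delivery record to missing would discard known non-events and push the estimated risk up.

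The cost is a few lines of SAP text and the matching code. The data are already collected.
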